1.4.1 Remapping rule

Subjects who received treatment as per protocol version 03 or earlier, but were assigned to an end of study day as per protocol version v04 and later (i.e., Day 270, Part 2), their end of study day will be remapped using the following rule: if the actual day of visit occurred is closer to the

planned day of end of study (i.e., Day 180, Part 1), then the planned day of end of study will be remapped to the end of study of Part 1, i.e. Day 180.

2 First interpretable results (FIR)

First interpretable results (FIR) will be provided for this trial.

Study outputs required to be created at the time of the FIR for interim and final analysis will be highlighted in Tables/Figures/Listings (TFL) shells document and marked as “Key” in the Programming Deliverables Tracker (PDT) output list.

FIR will focus on the following analyses for the final analysis:

- Subject disposition
- Demographics and baseline characteristics. Demographics and baseline characteristics include, but not limited to:
 - Age, Sex, Race, Weight, Height, BMI, Stratification factor (Asian/Non-Asian). The baseline characteristics table will include, among others, UPCR from 24hr urine collections (summary statistics as continuous variable and, by < 200 mg/mmol and \geq 200 mg/mmol group) and eGFR (summary statistics as continuous variable and, by <60 mL/min/1.73m² and \geq 60 mL/min/1.73m² group).
- Safety results
 - Number and percentage of subjects with adverse events (AEs) by body system organ class (SOC) and preferred term (PT) with a breakdown by treatment during the treatment period – Parts 1 and 2 to Day 90
 - Number and percentage of subjects with AEs by body system organ class (SOC) and preferred term (PT) with a breakdown by treatment during the treatment period – Part 2 patients on 180 days of treatment
 - Summary table of exposure adjusted treatment emergent AEs – Part 1 and Part 2
 - Number and percentage of subjects with treatment emergent serious AEs (SAEs), regardless of study drug relationship, by primary SOC and PT, with a breakdown by treatment – Parts 1 and 2 to Day 90
 - Number and percentage of subjects with treatment emergent SAEs, regardless of study drug relationship, by primary SOC and PT, with a breakdown by treatment – Part 2 patients on 180 days of treatment
 - Listing of SAEs and a listing of all AEs
 - Arithmetic mean (SD) profiles of hematology parameters over time by treatment group – Parts 1 and 2 to Day 90

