The full analysis set 1 (FAS1) will include all randomized patients in Part 1 and all randomized patients in Part 2 that consented to receive treatment as per protocol version 03 (i.e. allowing for 90 days of treatment) or earlier.

The full analysis set 2 (FAS2) will include all randomized patients in Part 2 that consented to receive treatment as per protocol version 04 or higher (i.e. allowing for 180 days of treatment). Mis-randomized patients, that is, patients who were incorrectly randomized and did not receive the study drug will be excluded from all FAS sets. For the full analysis sets, patients will be analyzed according to the treatment they have been assigned to at randomization. The full analysis sets will be used for the assessment of efficacy.

The safety analysis set (SAF) will include all randomized patients that received any study drug. The safety analysis set 1 (SAF1) will be likewise derived for patients in Part 1 and patients in Part 2 that consented to receive treatment as per protocol version 03 (i.e. allowing for 90 days of treatment) or earlier.

The safety analysis set 2 (SAF2) will be likewise derived for Part 2 that consented to receive randomized treatment as per protocol version 04 or higher (i.e. allowing for 180 days of treatment). For the safety analysis sets, patients will be analyzed according to the treatment they received.

The PK analysis set will include all subjects with at least one available valid (i.e. not flagged for exclusion) PK concentration measurement, who received any study drug and with no protocol deviations with relevant impact on PK data. For the PK analysis set, patients will be analyzed according to the treatment they received.

The PK1 analysis set will be likewise derived for patients in Part 1 and patients in Part 2 that consented to receive treatment as per protocol version 03 (i.e. allowing for 90 days of treatment) or earlier.

The PK2 analysis set will be likewise derived for Part 2 that consented to receive randomized treatment as per protocol version 04 or higher (i.e. allowing for 180 days of treatment).

The analysis sets and protocol deviation codes are related as follows:

Table 5-1: Protocol deviation codes and analysis sets

Category Deviation code	Text description of deviation	Data exclusion
Subjects are excluded from PK analysis in case of these PDs:		Exclude subject from PK, PK1 and PK2 analysis set
OTH20	Site has been closed down for GCP reasons	Yes

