Clinical laboratory evaluations

All laboratory data will be listed by treatment, subject, and visit/time and if normal ranges are available abnormalities will be flagged. A separate listing will be provided presenting all parameters in a subject with any abnormal values. Summary statistics will be provided by treatment and visit/time, for the SAF (up to Day 90) and for SAF1 and SAF2 separately. Summary statistics will include mean, SD, CV, Q1, median, Q3, minimum and maximum as appropriate. Values less than the Lower Limit (LL) will be imputed as $0.5 \times LL$ and values greater than the Upper Limit (UL) will be imputed as $1.5 \times UL$. The number and percentage of values below the LL and above the UL will be presented. For the figures, imputed values will be displayed.

Adverse events

All information obtained on adverse events will be displayed by treatment and subject. All information obtained on deaths will be likewise provided.

The overall incidence of treatment emergent AEs will be summarized by treatment group for the SAF (up to Day 90), SAF, SAF1 and SAF2 populations separately.

The number and percentage of subjects with adverse events will be tabulated by body system organ class (SOC) and preferred term (PT) with a breakdown by treatment, for the SAF (up to Day 90) and for SAF1 and SAF2 separately. A subject with multiple adverse events within a

body system is only counted once towards the total of this body system and treatment, for the event with highest severity. Summaries of SAEs will be provided in a similar manner.

A summary table of AEs leading to discontinuation of study treatment by preferred term will be produced for the SAF (up to Day 90), SAF1 and SAF2 separately.

Exposure-adjusted AE summaries will also be likewise considered for SAF.

For summary tables on exposure-adjusted AEs, the number of episodes per 100 patient months will be presented. The occurrence rate (number of episodes per 100 patient month) will be calculated as $100 \times (\text{the total number of AE episodes from all patients in the population divided by the total number of patient-months})$. A patient may have multiple occurrences of the same event. All occurrences are counted. Total patient months will be computed as $(\text{sum of the duration of exposure over patients, in days})/30.4375$. This method will account for the length of follow-up time under the assumption that events would occur with the same frequency at any point in time.

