In addition, 95% confidence intervals will be presented for the occurrence rate. It will be assumed that for each of n subjects the time t_j ($j=1, \dots, n$) represents the duration of exposure to study treatment. The sequence of occurrences of an event will be modeled to follow approximately a Poisson process with constant intensity θ . The rate parameter θ will be estimated as $\lambda = D/T$, where $T = \sum_{j=1}^n t_j$ and D is the total number of events. Conditionally on T , an exact $100 \times (1-\alpha)\%$ confidence interval for a Poisson variable with parameter θT and observed value D can be obtained based on (Garwood, 1936), from which an exact $100 \times (1-\alpha)\%$ confidence interval for $100 \times D/T$ will be derived as follows (Sahai, 1993):

Lower confidence limit $L = \frac{0.5c_{\alpha/2, 2D}}{T} * 100$ for $D > 0$, 0 otherwise,

Upper confidence limit $U = \frac{0.5c_{1-\alpha/2, 2D+2}}{T} * 100$ for $D > 0$, 0 otherwise,

where $c_{\alpha, k}$ is the α th quantile of the Chi-square distribution with k degrees of freedom.

Adverse events of special interest definitions are found in the compound electronic Case Retrieval Strategy (eCRS). The classification reflects the current version of the Development Safety Profiling Plan (DSPP) and might be updated based on review of accumulating data. A listing of the case retrieval strategy will be presented.

The frequency and percentage of patients with adverse events of special interest will be presented by MedDRA preferred term and treatment arm. These outputs will also be produced for the SAF (up to Day 90) and for SAF1 and SAF2 separately.

Further displays of AEs may be produced in order to appropriately describe the outcomes seen in this trial. For displays of Treatment Emergent events only, events will be considered as Treatment emergent if they started after the date of first administration of study treatment (or were present prior to start of study treatment but increased in severity based on preferred term) and up to 7 days after study treatment discontinuation. For post-treatment period, AEs and SAEs will be summarized separately for both SAF1 and SAF2 analysis sets.

For TEAE tables on SAF (Part 1 and Part 2 to Day 90) a cut-off of 90 + 7 days (post end of treatment) for Part 1 patients and Part 2 patients on 90 days of treatment will be used, whereas a cut-off of 90 days for Part 2 patients on 180 days of treatment will be used.

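### SAP 8.2 sets the upper 95% limit of an exposure-adjusted AE rate to 0 when no events occur, so a zero-event arm gets an interval of 0 to 0 instead of the exact Garwood interval

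*SAP*

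**What the plan says.** SAP Section 8.2, under Adverse events, expresses exposure-adjusted rates as episodes per 100 patient-months, with exposure in days divided by 30.4375. It then states: "In addition, 95% confidence intervals will be presented for the occurrence rate". Event counts are treated as Poisson with D events over total exposure T, and the exact "confidence interval for a Poisson variable with parameter θT and observed value D can be obtained based on (Garwood, 1936".

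The first of the two formulas reads "Lower confidence limit $L = \frac{0.5c_{\alpha/2, 2D}}{T} * 100$ for $D > 0$, 0 otherwise". For the other end of the interval, the SAP then writes "Upper confidence limit $U = \frac{0.5c_{1-\alpha/2, 2D+2}}{T} * 100$ for $D > 0$, 0 otherwise".

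Here c is a chi-square quantile with the stated degrees of freedom. The same condition is attached to both lines, and no other part of the protocol or SAP sets a different rule for D = 0.

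On where the intervals are used, Section 8.2 says: "Exposure-adjusted AE summaries will also be likewise considered for SAF". SAP Section 2 lists among the first interpretable results a "Summary table of exposure adjusted treatment emergent AEs" covering Parts 1 and 2.

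**The concern.** The condition is needed for the lower limit, because a chi-square with 2D = 0 degrees of freedom is degenerate and the exact lower limit is 0. It does not belong on the upper limit, where the degrees of freedom are 2D + 2 = 2 when D = 0. Setting that limit to 0 contradicts the exact interval announced just before it.

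A program that follows the formulas literally prints 0 to 0 for any arm or event term with no events. A program that follows the named method prints a positive upper limit. Two programmers working independently could therefore disagree, each with support in the text.

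The error matters where the trial is least informative. Arms hold roughly 20 patients, and the protocol's potential risks include serious infections and bone marrow toxicity (Protocol Sections 3.6.2.1 and 3.6.2.3). When none of a rare event is seen, the upper limit is the informative part of the result. An interval of 0 to 0 also makes a zero-event arm look fully separated from an arm of the same size with one event.

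**Working it through.** **Inputs from the documents.** Two-sided 95% level (α = 0.05), the Garwood form and the month conversion are from SAP 8.2. The Part 1 allocation of 14, 10, 10 and 14, the roughly 50 patients in Part 2, the aim of equal allocation over the whole study and the treatment durations of 90 and 180 days are from SAP 1.4.

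**The formulas where they are right.** At D = 1 the limits in expected events are 0.5·χ²(0.025; 2) = 0.0253 and 0.5·χ²(0.975; 4) = 5.572. The tail probability at each limit is exactly 0.025. The same check holds at D = 3. For D > 0 the SAP is correct.

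**At D = 0.**

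- As written: lower 0, upper 0.
- From the SAP's own upper expression: 0.5·χ²(0.975; 2) = −ln(0.025) = 3.689 events, which is 368.9/T per 100 patient-months.
- Placing the whole 5% in the upper tail would give −ln(0.05) = 2.996. This variant does not give 0 either.

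**Illustrative size.** Assume 98 patients, 19.6 per arm, full planned exposure, and 180 days for every Part 2 patient.

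| Arm | T (patient-months) | Upper limit at D = 0, per 100 patient-months |
|---|---|---|
| Placebo, 200 mg | (14×90 + 5.6×180)/30.4375 = 74.51 | 368.89/74.51 = 4.95 |
| 10 mg, 50 mg | (10×90 + 9.6×180)/30.4375 = 86.34 | 368.89/86.34 = 4.27 |
| 100 mg | 19.6×180/30.4375 = 115.91 | 368.89/115.91 = 3.18 |
| Any arm, if all had 90 days | 19.6×90/30.4375 = 57.95 | 368.89/57.95 = 6.37 |

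The last row is an extreme case. SAP Section 5 provides for Part 2 patients who "consented to receive treatment as per protocol version 03 (i.e. allowing for 90 days of treatment) or earlier", but does not say how many there were.

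**Comparison with one event.** At T = 74.51 and D = 1, the rate is 100/74.51 = 1.34, with limits 100×0.0253/74.51 = 0.03 and 100×5.572/74.51 = 7.48. As written, the zero-event interval of 0 to 0 lies wholly below this. In expected events the correct intervals are 0 to 3.689 and 0.025 to 5.572. Their overlap of 3.664 is 99% of the zero-event interval and 66% of the one-event interval.

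**Coverage.** For a true expected count μ above 0 and up to 3.689, the correct D = 0 interval covers μ and the SAP's does not, so coverage drops by P(D = 0) = e^(−μ). At μ = 0.5 the intervals for D = 0, 1 and 2 should cover: e^(−0.5)(1 + 0.5 + 0.125) = 98.6%. Removing D = 0 takes away 60.7 points and leaves 37.9%.

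| Expected count | As written | Upper formula applied at D = 0 |
|---|---|---|
| 0.1 | 9.1% | 99.5% |
| 0.5 | 37.9% | 98.6% |
| 1 | 61.3% | 98.1% |
| 2 | 84.8% | 98.3% |
| 3 | 93.8% | 98.8% |
| 3.7 and above | identical | identical |

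**The case against.** The best case on the other side is that this is a misplaced condition in a descriptive table. Every interval with D > 0 and every point estimate is right, no decision rule uses these intervals, and the paragraph names the method from which the correction follows. The first-interpretable-results entry does not mention system organ class or preferred term, whereas the neighbouring adverse event entries do. If that table reports only all events per arm, a count of zero in about 20 patients followed for 3 to 6 months is unlikely and nothing would change. The arm-level figures also rest on assumed arm sizes and full exposure. Protocol Section 11.7 allows for drop-out of up to 20%, and a 20% loss of exposure would raise each limit by a quarter (6.37 would become about 8.0).

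Most of this is fair and limits the reach of the point. The number of affected rows cannot be known without the table shells, although Section 8.2 introduces the exposure-adjusted summaries right after the tabulation by organ class and preferred term, so rows by term are plausible. The arm figures are illustrations, not bounds. None of this defends the upper limit at D = 0: the result 368.9/T needs no assumption about exposure, and the formula as written contradicts the method it claims to implement.

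**Conclusion.** The concern holds. For any cell with no events, SAP 8.2 as written yields 0 to 0 where the exact 95% interval is 0 to 368.9/T per 100 patient-months. Under the stated illustrative assumptions the missing upper limit is about 3.2 to 5.0, or 6.4 if all patients had 90 days; lower exposure would make it larger. Coverage is well below nominal when fewer than about 2 events are expected, is slightly low at 3, and is unaffected from about 3.7. The consequence is confined to zero-event cells of descriptive safety output, and the primary analysis is untouched. It should still be corrected, because it understates uncertainty about rare harms in small arms.

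**What to change.** In SAP 8.2, leave the zero clause on the lower limit and delete it from the upper limit, stating that the upper formula applies for all D ≥ 0. State also that T is in patient-months, so that the limits are on the same scale as the reported rate. Make the same change in the table program and check one zero-event cell against 368.9/T. The cost is one line in the SAP and one in the code, with no new data. SAP Section 8 already schedules the safety analyses to be rerun after database lock, so the correction fits into planned work.

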3.6.2.5 Non-clinical safety findings of undetermined relevance

In toxicology studies with LNP023, a few findings were observed that are considered of undetermined relevance based on current knowledge. These have not been seen in the clinical setting thus far, and there is no evidence to conclude that these have a causal association with LNP023 exposure or an impact on the risk-benefit balance of LNP023.

Cardiovascular effects: LNP023 in medium to high doses in dogs elicited peripheral vasodilatation, reducing the total peripheral resistance and blood pressure in addition to causing compensatory heart rate increase. At the highest doses, pathological changes were noted in the dogs. The response may be present in humans, even though it was not seen in other species. Small QTc effects were observed at high doses and exposures in nonhuman primates, but in no other species. The risk for humans is considered to be small, but vital signs, ECGs and cardiac AEs will be closely monitored. See [Section 8.6.7](#)

Hyperbilirubinemia: In the 4-week GLP toxicological study, a significant dose-dependent effect was observed on the conjugated bilirubin levels in rats and dogs. The effect was considered to be minimal to mild. No change was observed in liver enzymes and the effect was reversible in all animals. Increased bilirubin was accompanied by bile duct hyperplasia in one high-dose dog. At this point it is not known if the hyperbilirubinemia is translatable to humans. Liver function tests and hepatic AEs will be closely monitored in the LNP023 program. See [Section 8.6.8](#).

Proteinuria: This finding was observed in rats treated with high doses of LNP023 (1,000 mg/kg), but electron microscopy did not reveal any morphological changes. The effect was fully reversible, and morphological changes and proteinuria were not observed in dogs. Urine and renal function will be closely monitored. See [Section 8.8.4](#)

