3.6.3 Risk mitigation strategy

Safety and tolerability data for LNP023 doses up to 200 mg b.i.d. have been collected in study LNP023X2101 in HV, [Section 3.6.2](#). There are four potential risks that have been identified namely ‘infections’ and ‘testicular effects’, ‘bone marrow toxicity and severe anaemia’ and ‘thyroid follicular cell hypertrophy’. Infection is mitigated by vaccinations against encapsulated bacteria as described in [Section 3.6.2.1](#). The testicular risk is carefully monitored by analyzing the level of relevant hormones (see [Section 3.6.2.2](#)). The bone marrow risk is monitored by review of haematological laboratory values and AEs. Thyroid function will be regularly measured by TSH, T3, T4 and reversed T3. Furthermore, there are preclinical findings of undetermined clinical relevance that will be mitigated by careful clinical monitoring. Thus, blood pressure and 12-lead ECG will be monitored before and after the first dose and before and after a dose at steady state (Day 30) and at other visits throughout the study. Bilirubin and liver enzymes will be carefully monitored together with other laboratory parameters. Finally, urine will repeatedly be collected for analysis of proteinuria as well as other biomarkers in urine.

Patients will return to the clinic on a regular basis. During these visits safety, tolerability, efficacy and PK/PD data will be collected. Standard safety assessments will include vital signs, physical examinations, ECGs, clinical laboratory evaluations (hematology, blood chemistry and urinalysis), and AEs as outlined in the [Assessment schedule \(Table 8-1\)](#).

A priori defined stopping criteria and guidelines ([Section 7.5](#)) in addition to the clinical opinion of the Investigator will be used to protect individual patient safety during the trial.

Finally, key safety data will be reviewed by the Sponsor and DMC in a blinded manner on an ongoing basis.

4 Population

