9.1 Adverse events

An AE is any untoward medical occurrence (i.e., any unfavorable and unintended sign [including abnormal laboratory findings], symptom or disease) in a subject after providing written informed consent for participation in the study until the end of study visit. Therefore, an AE may or may not be temporally or causally associated with the use of a medicinal (investigational) product.

In addition, all reports of intentional misuse and abuse of the study treatment are also considered an adverse event irrespective if a clinical event has occurred. See [Section 9.5](#) for an overview of the reporting requirements.

The occurrence of AEs must be sought by non-directive questioning of the subject at each visit during the study. Adverse events also may be detected when they are volunteered by the subject during or between visits or through physical examination finding, laboratory test finding, or other assessments.

Abnormal laboratory values or test results constitute adverse events only if they fulfill at least one of the following criteria:

- they induce clinical signs or symptoms,
- they are considered clinically significant,
- they require therapy.

Clinically significant abnormal laboratory values or test results should be identified through a review of values outside of normal ranges/clinically notable ranges, significant changes from baseline or the previous visit, or values which are considered to be non-typical in patients with underlying disease. Investigators have the responsibility for managing the safety of individual subject and identifying adverse events. Alert ranges for liver events are included in [Appendix 1](#).

Adverse events should be recorded on the appropriate CRF capturing AEs under the signs, symptoms or diagnosis associated with them, and accompanied by the following information:

1. The severity grade
 - mild: usually transient in nature and generally not interfering with normal activities
 - moderate: sufficiently discomforting to interfere with normal activities
 - severe: prevents normal activities
2. its relationship to the study treatment
3. its duration (start and end dates) or if the event is ongoing an outcome of not recovered/not resolved must be reported.
4. whether it constitutes a SAE (see [Section 9.2](#) for definition of SAE) and which seriousness criteria have been met
5. Action taken regarding investigational treatment.

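### The treatment-emergent rule in SAP 8.2 requires onset after the date of first dosing, so new post-dose events on Day 1 fall outside every display restricted to treatment-emergent events

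*SAP*

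**What the plan says.** SAP 8.2 (Adverse events) holds the only definition of treatment-emergent in the two documents. It applies "For displays of Treatment Emergent events only" and states that "events will be considered as Treatment emergent if they started after the date of first administration of study treatment". There is one alternative route, for events that "were present prior to start of study treatment but increased in severity based on preferred term". The window closes "up to 7 days after study treatment discontinuation". In the pooled Day 90 tables, "a cut-off of 90 days for Part 2 patients on 180 days of treatment will be used".

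Protocol 3.1 and SAP 1.4 both place first dosing on Day 1. Protocol 9.1 asks for each event's timing as "its duration (start and end dates) or if the event is ongoing" and names no onset time. Neither document has an on-or-after clause, or a rule for events that start on the day of first dosing.

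SAP 8.2 (Treatment) computes exposure as last dosing date minus first dosing date plus 1, so Day 1 is an exposure day.

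**The concern.** The boundary sits one calendar day too late. A new event in the hours after the first dose is what a treatment-emergent flag should catch, yet its start date equals the first-dose date and the rule asks for a later one. The worsening route cannot admit it, because it was not present before treatment. It is not a post-treatment event either.

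The plan itself treats Day 1 as informative. Protocol 3.6.3 states that "blood pressure and 12-lead ECG will be monitored before and after the first dose", against the background in Protocol 3.6.2.5 that the drug in dogs "elicited peripheral vasodilatation, reducing the total peripheral resistance and blood pressure in addition to causing compensatory heart rate increase". Under the footnotes to the assessment schedules, dosing is twice daily from Day 1, with the morning dose at the site and the evening dose at home. The excluded day therefore normally covers the first two doses. SAP 8.2 describes the post-dose blood pressure and heart-rate readings as falling near the time of peak concentration.

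At stake is whether the treatment-emergent summaries, including the public disclosure tables, are complete for new events on the first day of exposure.

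**Working it through.** The plan states no figure that depends on this rule, so there is none to reproduce. The check applies the rule as written and then counts days.

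**Step 1. Apply the definition to each type of onset.**

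| Onset | Start date after first-dose date? | Present before treatment and worsened? | Treatment-emergent as written? |
|---|---|---|---|
| New, Day 1, after the dose | No (dates equal) | No | No |
| New, Day 2 or later, within the window | Yes | Not needed | Yes |
| Present before treatment, worsens on treatment | No | Yes | Yes |
| Before the dose, no worsening | No | No | No |

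Only the first row gives a wrong classification. The gap is exactly one calendar day.

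**Step 2. Find the displays that carry the restriction.** Those labelled treatment-emergent are:
- overall TEAE incidence (SAP 8.2);
- treatment-emergent SAEs by SOC and PT (SAP 2);
- exposure-adjusted TEAEs (SAP 2);
- the two ClinicalTrials.gov/EudraCT disclosure tables (SAP 8.2).

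**Step 3. Count the days lost.** Days lost are the window starting on Day 1 minus the window starting on Day 2.
- 90-day treatment plus 7 days: Day 1 to Day 97 is 97 days; Day 2 to Day 97 is 96 days. Lost: 1/97 = 1.0%.
- 180-day patients in the Day 90 tables: Day 1 to Day 90 is 90 days; Day 2 to Day 90 is 89 days. Lost: 1/90 = 1.1%.
- 180-day patients over the full window: 180 + 7 = 187 days, of which 186 are covered. Lost: 1/187 = 0.5%.

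These are also the expected shares of new events lost if events arise at a constant rate. If they cluster at the first dose the share is higher. New post-dose events confined to Day 1 are all lost from these displays, but that restates the rule and is not an estimate of impact.

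**Step 4. Check the exposure-adjusted rate.** SAP 8.2 uses 100 × D/T, with T the sum of exposure days divided by 30.4375. A patient dosed for 90 days contributes 90/30.4375 = 2.96 patient-months, and Day 1 is 1/90 = 1.1% of that. For a patient dosed for 180 days it is 1/180 = 0.6%. In the treatment-emergent version of this table, D omits new Day 1 events while T includes the day on which they arose, so numerator and denominator cover different periods.

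**The case against.** The strongest reply concerns reach. The rule binds only displays restricted to treatment-emergent events. In SAP 8.2 the main SOC/PT table, the table of events leading to discontinuation and the special-interest table are described as tables of adverse events, without that label. In SAP 2 and SAP 3 the SOC/PT tables cover the treatment period, which begins on Day 1. As described, a Day 1 event stays in those by-arm counts and in the listings. This stands, with one caution: SAP 8.2 also refers to TEAE tables on the pooled safety set without naming them, and the table shells that would settle which tables carry the flag are not in the documents.

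The acute haemodynamic question also has its own analysis. SAP 8.2 plots Day 1 post-dose blood pressure and heart rate by treatment, relates their changes to peak concentration, and tabulates ECG abnormalities by treatment and timepoint. None of this uses the flag. Protocol 3.6.2 adds that healthy volunteers given single doses up to 400 mg had few events, mostly mild and about as frequent as on placebo, with no clinically relevant change in blood pressure or pulse. Protocol 3.6.2.5 says the dog findings had not been seen clinically. These points stand and limit the likely impact.

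Two further replies stand in part. The sentence may have been meant to divide time at the start of treatment, with no deliberate Day 1 gap; but a programmer follows the written rule, so an intended meaning that differs from it is a reason to correct the text. The case report form might record an onset time, which the documents do not show; but the rule as worded compares against a date, so a recorded time would not change the result.

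A reader might go further and infer that the safety comparison across doses is biased towards no difference. The documents do not support that. They give no Day 1 event rate and no sign that such events are dose-related, and by-arm counts remain in the tables not restricted to treatment-emergent events.

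**Conclusion.** The rule gives a wrong result when followed literally. New post-dose events on Day 1 are left out of overall TEAE incidence, treatment-emergent SAEs, exposure-adjusted TEAEs and the disclosure tables. In the exposure-adjusted table the same day is still counted as exposure.

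The size is modest on what can be known. At a constant event rate the loss is about 0.5% to 1% of the window, depending on treatment duration and table. It is larger only if events cluster at the first dose, and the actual number cannot be computed from the documents.

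The conclusion rests on the literal date comparison and on the absence of any other definition in the protocol or SAP. It does not extend to all adverse event reporting: the listings, the AE tables not labelled treatment-emergent and the Day 1 vital-sign and ECG displays are unaffected. This is a small defect in an important definition, and a cheap one to correct.

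**What to change.** Reword the first condition in SAP 8.2 so that a new event is treatment-emergent if its onset is on or after the date (and time, where recorded) of the first dose. Add that a Day 1 event of unknown clock time counts as treatment-emergent unless the record shows that it began before the dose. Apply the rule to all treatment-emergent displays, including the SAE, exposure-adjusted and disclosure tables, and state in the table shells which AE tables carry the flag.

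The cost is a short SAP edit and one programming condition. No efficacy analysis is touched, and SAP 8 already plans to rerun the safety analyses after database lock. The downside is that a few Day 1 events that began before the dose may be counted. Under blinded randomised treatment this is not expected to differ between arms.
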